Appendix I: ACCRU-ICRN-1702 Patient Drug Diary

Name:	Patient ID Number:
Cycle:	
You will take ____ tabs in the MORNING and ____ tabs in the EVENING.	

ORAL MEDICATION DIARY**Patient Instructions**

- Please bring your Medication Diary and any empty or unused medication container(s) with you to every appointment
- Please use an ink pen when completing the Medication Diary as these will be retained in our research record.
- Please contact your physician and study coordinator any time you go into the hospital. Your physician can advise if you should stop taking your medication or continue it.
- To correct an error or mistake, please make a single line through that entry and write your initials and date next to the error or mistake.
- Please record each dose as soon as you take it and fill in the date as directed.
- Please indicate on the calendar below every day you take your study medications by placing the time dose was taken on the line under the date.
- If you miss a dose, place a check "0" under the date, but remember to take your prescribed dose at the next regularly scheduled time.
- Take tablets by mouth daily as prescribed on days 1-28 of each cycle.
- If you accidentally take more than you are instructed to, contact your doctor or the emergency room immediately.
- If you miss a dose, do not make up the dose or double up on the next dose.

	Day 1	Day 2	Day 3	Day 4	Day 5	Day 6	Day 7
Date:							
Time of Morning Dose	AM	AM	AM	AM	AM	AM	AM
Time of Evening Dose	PM	PM	PM	PM	PM	PM	PM
	Day 8	Day 9	Day 10	Day 11	Day 12	Day 13	Day 14
Date:							
Time of Morning Dose	AM	AM	AM	AM	AM	AM	AM
Time of Evening Dose	PM	PM	PM	PM	PM	PM	PM
	Day 15	Day 16	Day 17	Day 18	Day 19	Day 20	Day 21
Date:							
Time of Morning Dose	AM	AM	AM	AM	AM	AM	AM
Time of Evening Dose	PM	PM	PM	PM	PM	PM	PM
	Day 22	Day 23	Day 24	Day 25	Day 26	Day 27	Day 28
Date:							
Time of Morning Dose	AM	AM	AM	AM	AM	AM	AM
Time of Evening Dose	PM	PM	PM	PM	PM	PM	PM

APPENDIX II: OLAPARIB SAFETY DATA EXCHANGE REQUIREMENTS

1. STUDY IDENTIFICATION

Sponsor/Sponsor-Investigator:	<< insert name of Sponsor/Sponsor-Investigator>>
Sponsor/Sponsor-Investigator <<Study Title>> <<Study No.>>	<< Insert Study Title and/or Study No. and/or Project title>>
AstraZeneca reference <<study/project>> number(s)	<<Insert AstraZeneca ESR tracking number and D-code>>
Sponsor/Sponsor-Investigator Study/project acronym:	<<Insert Study or project acronym>>

See summary table at the end of this document for further details

2. Before the study starts

Sponsor/Sponsor-Investigator will provide AstraZeneca with:

- A copy of the format of the (S)AE report form and cover letter, for reporting from investigator to sponsor. SAE form and/or cover letter must include the AstraZeneca Reference number(s).

An example of the format by which SAEs (including SUSARS) and AESIs will be reported from sponsor to AstraZeneca. This may be the same form used for reporting SAEs as above. This must include the AstraZeneca ESR Tracking number and contact details for reporting to AstraZeneca (e-mail address or fax number e.g.

[REDACTED]

- The format by which site and patient ID will be presented in safety data so that they can be entered in a consistent way on the AstraZeneca safety database.

Please provide here: _____

- The Development International Birth Date (DIBD) for the IMP, for the Sponsor/Sponsor-Investigator Development Safety Update Report (DSUR):
 - <<enter DIBD>>

The DIBD is the date of the sponsor's first authorisation to conduct a clinical study with the IMP or IMP combination

AstraZeneca will provide the Sponsor/Sponsor-Investigator with:

- The current IB and Protocol Guidelines, which identifies Olaparib AEs of Special Interest (AESIs). Section 5.4 of the IB provides details of the expectedness of AEs.

This is only applicable when the medicinal product under study is not marketed in the country(ies) where the study is being conducted. For marketed products the local label is used and the above can be deleted.

- AstraZeneca DIBD for the IMP, for AstraZeneca DSUR:
 - << enter AstraZeneca DIBD>>

3. Safety data exchange during the study

3.1 Sponsor/Sponsor-Investigator will provide AstraZeneca with:

3.1.1 Individual ICSR data

- Report unblinded Suspected Unexpected Serious Adverse Reactions (SUSARs) to AstraZeneca as individual case reports as they occur and in parallel to reporting to the regulatory authority.

Select the appropriate bullet(s) from the list below ensuring that all other (S)AEs (both related and unrelated) are accounted for as applicable to the study type (refer to SOP Clinical Externally Sponsored Scientific Research, LDMS_001_00201128).

- Report Serious Adverse Events (SAEs) including Suspected Serious Adverse Reactions (SSARs) to AstraZeneca as individual case reports on an ongoing basis as they occur
- Report Serious Adverse Events (SAEs) including Suspected Serious Adverse Reactions (SSARs) to AstraZeneca in a blinded listing

- Promptly respond to follow up questions from AstraZeneca Data entry site

The following essential information must be provided to AstraZeneca in SUSAR, SSAR and SAE reports (initial and follow-up):

- AstraZeneca tracking number
- <<Sponsor/Sponsor-Investigator study number>>
- <<Centre number (if applicable)>>
- Patient study number
- Age
- Sex
- IMP(s) dose, start & stop date
- SAE onset & stop date
- Event term as reported by the investigator and/or the CTCAE V4 term
- <<CTCAE grade for oncology studies, as applicable>>
- Investigator's assessment of seriousness, according to ICH definitions
- Investigator's assessment of causality
- SAE Outcome
- Date of death, if applicable

Note: The Study tracking number must be provided in the header of the cover note << and also in the e-mail Subject>>. If possible the study tracking number may also be included in the (S)AE form.

3.1.2 Line listings

Line listings of SUSARs, SSARs and SAEs will:

- Be provided on a monthly basis for Phase I studies, otherwise quarterly.
- SUSARs included in the listings should be easily identifiable.
- Contain only updated information since the last listing.

Cumulative final listings will be provided at clean file for the primary analysis and after the last patient has completed the study.

3.1.3 Other safety information

- Inform AstraZeneca within 24 hours of knowledge of any emerging safety issue, unanticipated problem or actions that the Sponsor/Sponsor-Investigator is considering as a result of a safety signal with the IMP. This includes but is not limited to:
 - Urgent safety measures to be implemented in the study

- Safety amendments to protocol/patient information & informed consent
- Open reports from Independent Data Monitoring Committees (IDMCs) excluding confidential reports to IDMC and minutes of IDMC meetings
- Interactions with Regulatory Authorities (RAs)/ Ethics Committees (ECs)
- Inform AstraZeneca on an ongoing basis of any new safety trends or signals observed during routine safety surveillance activities.

This information will be included in the *quarterly* progress reports submitted to ESSROS.

- Inform AstraZeneca on an ongoing basis of any new safety trends or signals observed during routine safety surveillance activities.

3.2 AstraZeneca will:

- Provide IB updates during the course of the study.
- Immediately inform the Sponsor/Sponsor Investigator of any emerging safety issue, unanticipated problem or actions that AstraZeneca is considering as a result of a safety signal with the IMP. This includes but is not limited to:
 - New safety information which may alter the benefit risk assessment
 - Urgent safety measures to be implemented
- Request follow-up information on SUSAR, SAEs, SSARs and AESIs.
- Consult with the Sponsor/Sponsor-Investigator in the unlikely circumstance that code break information is required for an individual patient, because AstraZeneca need to expedite an SAE that has not been unblinded by the Sponsor/Sponsor-Investigator.

4. At the end of the study

At the end of the study the Sponsor/Sponsor-Investigator will:

- Provide AstraZeneca with the final study report containing details of all AEs.

5. SUMMARY OF REQUIREMENTS FOR ROUTINE EXCHANGE OF SAFETY DATA

5.1 Sponsor/Sponsor-Investigator will report safety information to AstraZeneca:

Report Type	Report format	When to send report to AstraZeneca	Method of Submission	Additional Information
SUSARs	Individual unblinded case reports (Initial and follow-up reports)	In parallel to submission to the concerned RA	
[REDACTED]
 
Or
 
[REDACTED]
 
If secure e-mail is in place.
	
Sponsor/Sponsor-Investigator responsible for:
 
 Expedited reporting of all SUSARs to the Regulatory Authority(RA) of participating countries in line with local requirements. Compliance with local regulations of participating countries for reporting of SUSARs to investigational sites and EC's. 
AstraZeneca is responsible for:
 
 Reporting SUSARs to RA's where Company sponsored studies are being conducted with the IMP as appropriate or where the product is marketed. Reporting SUSARs to Sponsor/Sponsor-investigators participating in any Company sponsored studies

				with the IMP as required by RA's.
SAEs (including SSARs)	Individual blinded case reports (Initial and follow-up reports)	Within 15 days from awareness of event	As above	
Report Type	Report format	When to send report to AstraZeneca	Method of Submission	Additional Information
Annual report	Periodic safety report (produced for external purposes e.g EC or RA of participating countries)	Only required if inconsistent with the IB/Label.	Sponsor/Sponsor-Investigator provides to ESR Coordinator. ESR Coordinator forwards to SSaMT	Examples of reports in this category include Development Safety Update Reports (DSUR) and IND update reports. Any findings that are inconsistent with the IB/Label shall be communicated to AstraZeneca during production of the report but at the latest in parallel to submission to the RA/Ethics committee.


End of Study
 
SAEs, SSARs & SUSARs (for entry onto AZ Patient Safety database)
	
A cumulative final listing of all unblinded SAEs, SSAR's & SUSARs
	
At clean file* at the following time points:
 
 1. At primary analysis 2. After last patient has completed study treatment. 	
[REDACTED]
 
[REDACTED]
 
[REDACTED]
 
If secure e-mail is in place
	
AstraZeneca require a listing of all adverse events reported during the study, for the purpose of reconciliation. This list shall preferably be unblinded to also allow unblinding of the events on AstraZeneca safety database.
 
*Clean file means when all study queries have been answered and the database is locked.
 
For convenience and completeness SUSARs should also be included and easily identifiable.

--	---	--	---	--

5.2 AstraZeneca will submit the following safety information to the Sponsor/Sponsor-Investigator:

Report Type	Report format	When to send report from AstraZeneca	Method of Submission	Additional Information

SUSARs (from company sponsored studies and other sources)
	
Blinded Periodic SUSAR Line Listing (PSLLs)- OR 'No SUSAR' notification
	
Six monthly
	
Email to Sponsor/Sponsor-Investigator
 
(only if secure dataexchange is in place), otherwise a hard copy to be sent via mail
	
 • In Europe these will only be provided while AstraZeneca still has patients in Company sponsored studies or until the IMP becomes marketed • AstraZeneca will provide the Company PSLLs produced for Company reporting obligations, to Sponsor/Sponsor-investigators in parallel to Company reporting to EC's and relevant RAs involved in Company sponsored studies. • Sponsor/Sponsor-Investigator will distribute these to Sponsor-investigators and ECs

				in line with local requirements.
--	--	--	--	----------------------------------

6. CONTACT DETAILS

AstraZeneca

Study Coordinator:

Name:

Email:

Telephone:

Patient Safety Data Entry site

Sponsor/Sponsor-Investigator:

Periodic line listings notification:

Name:

Email:

Telephone:

SAE follow-up queries:

Name:

Email:

<<Fax>>

Telephone:

Unblinding requests:

Name:

Telephone:

AstraZeneca tracking number and IMP name(s) shall be included in email headers and secure data exchange transfer must be in place.

Information compiled by:

Signature _____ Date _____

Name	Title
------	-------

Appendix III: Actions required in cases of increases in liver biochemistry and evaluation of Hy's Law

A 1 Introduction

This Appendix describes the process to be followed in order to identify and appropriately report cases of Hy's Law. It is not intended to be a comprehensive guide to the management of elevated liver biochemistries.

During the course of the study the Investigator will remain vigilant for increases in liver biochemistry. The Investigator is responsible for determining whether a patient meets potential Hy's Law (PHL) criteria at any point during the study.

The Investigator participates, together with AstraZeneca clinical project representatives, in review and assessment of cases meeting PHL criteria to agree whether Hy's Law (HL) criteria are met. HL criteria are met if there is no alternative explanation for the elevations in liver biochemistry other than drug induced liver injury (DILI) caused by the investigational medicinal product (IP).

The Investigator is responsible for recording data pertaining to PHL/HL cases and for reporting Adverse Events (AE) and Serious Adverse Events (SAE) according to the outcome of the review and assessment in line with standard safety reporting processes.

A 2 Definitions

Potential Hy's Law (PHL)

Aspartate aminotransferase (AST) or alanine aminotransferase (ALT) $\geq 3 \times$ upper limit of normal (ULN) **together with** total bilirubin (TBL) $\geq 2 \times$ ULN at any point during the study following the start of study medication irrespective of an increase in alkaline phosphatase (ALP).

Hy's Law (HL)

AST or ALT $\geq 3 \times$ ULN **together with** TBL $\geq 2 \times$ ULN, where no other reason, other than the IMP, can be found to explain the combination of increases, eg, elevated ALP indicating cholestasis, viral hepatitis, another drug.

For PHL and HL the elevation in transaminases must precede or be coincident with (ie, on the same day) the elevation in TBL, but there is no specified time frame within which the elevations in transaminases and TBL must occur.

A 3 Identification of potential Hy's Law cases

In order to identify cases of PHL it is important to perform a comprehensive review of laboratory data for any patient who meets any of the following identification criteria in isolation or in combination:

- $ALT \geq 3 \times ULN$
- $AST \geq 3 \times ULN$
- $TBL \geq 2 \times ULN$

The Investigator will also remain vigilant for any local laboratory reports where the identification criteria are met, where this is the case the Investigator will:

- Notify the AstraZeneca representative
- Request a repeat of the test (new blood draw) by the local laboratory
- Complete the appropriate unscheduled laboratory CRF module(s) with the original local laboratory test result

When the identification criteria are met from central or local laboratory results the Investigator will without delay:

- Determine whether the patient meets PHL criteria (see Appendix A2 for definition) by reviewing laboratory reports from all previous visits

The Investigator will without delay review each new laboratory report and if the identification criteria are met will:

- Notify the AstraZeneca representative
- Determine whether the patient meets PHL criteria (see Appendix A2 for definition) by reviewing laboratory reports from all previous visits
- Promptly enter the laboratory data into the laboratory CRF

A 4 Follow-up

A 4.1 Potential Hy's Law criteria not met

If the patient does not meet PHL criteria the Investigator will:

- Inform the AstraZeneca representative that the patient has not met PHL criteria.

- Perform follow-up on subsequent laboratory results according to the guidance provided in the Clinical Study Protocol.

A 4.2 Potential Hy's Law criteria met

If the patient does meet PHL criteria the Investigator will:

Determine whether PHL criteria were met at any study visit prior to starting Study treatment

- Notify the AstraZeneca representative who will then inform the central Study Team

The Study Physician contacts the Investigator, to provide guidance, discuss and agree an approach for the study patients' follow-up and the continuous review of data. Subsequent to this contact the Investigator will:

- Monitor the patient until liver biochemistry parameters and appropriate clinical symptoms and signs return to normal or baseline levels, or as long as medically indicated
- Investigate the aetiology of the event and perform diagnostic investigations as discussed with the Study Physician.
- Complete the three Liver CRF Modules as information becomes available
- If at any time (in consultation with the Study Physician the PHL case meets serious criteria, report it as an SAE using standard reporting procedures.

A 5 Review and assessment of potential Hy's Law cases

The instructions in this section should be followed for all cases where PHL criteria are met.

No later than 3 weeks after the biochemistry abnormality was initially detected, the Study Physician contacts the Investigator in order to review available data and agree on whether there is an alternative explanation for meeting PHL criteria other than DILI caused by the IMP. The AstraZeneca Global Clinical Lead or equivalent and Global Safety Physician will also be involved in this review together with other patient matter experts as appropriate.

According to the outcome of the review and assessment, the Investigator will follow the instructions below.

If there is an agreed alternative explanation for the ALT or AST and TBL elevations, a determination of whether the alternative explanation is an AE will be made and subsequently whether the AE meets the criteria for a SAE:

- If the alternative explanation is **not** an AE, record the alternative explanation on the appropriate CRF
- If the alternative explanation is an AE/SAE, record the AE /SAE in the CRF accordingly and follow the AZ standard processes

If it is agreed that there is **no** explanation that would explain the ALT or AST and TBL elevations other than the IMP:

- Report an SAE (report term ‘Hy’s Law’) according to AstraZeneca standard processes.
 - The ‘Medically Important’ serious criterion should be used if no other serious criteria apply
 - As there is no alternative explanation for the HL case, a causality assessment of ‘related’ should be assigned.

If there is an unavoidable delay of over 3 weeks in obtaining the information necessary to assess whether or not the case meets the criteria for HL, then it is assumed that there is no alternative explanation until such time as an informed decision can be made:

- Report an SAE (report term ‘Potential Hy’s Law’) applying serious criteria and causality assessment as per above
- Continue follow-up and review according to agreed plan. Once the necessary supplementary information is obtained, repeat the review and assessment to determine whether HL criteria are met. Update the SAE report according to the outcome of the review amending the reported term if an alternative explanation for the liver biochemistry elevations is determined.

A 6 Actions required when potential Hy’s Law criteria are met before and after starting study treatment

This section is applicable to patients with liver metastases who meet PHL criteria on Study treatment having previously met PHL criteria at a study visit prior to starting Study treatment. At the first on-study treatment occurrence of PHL criteria being met, the Investigator will determine if there has been a significant change in the patients’ condition compared with the last visit where PHL criteria were met.

- If there is no significant change, no action is required
- If there is a significant change, notify the AstraZeneca representative, who will inform the central Study Team,

- A ‘significant’ change in the patient’s condition refers to a clinically relevant change in any of the individual liver biochemistry parameters (ALT, AST or total bilirubin) in isolation or in combination, or a clinically relevant change in associated symptoms. The determination of whether there has been a significant change will be at the discretion of the Investigator, this may be in consultation with the Study Physician if there is any uncertainty.

A 7 Actions required for repeat episodes of potential Hy’s Law

This section is applicable when a patient meets PHL criteria on study treatment, and has already met PHL criteria at a previous on study treatment visit.

The requirement to conduct follow-up, review, and assessment of a repeat occurrence(s) of PHL is based on the nature of the alternative cause identified for the previous occurrence.

The investigator should determine the cause for the previous occurrence of PHL criteria being met and answer the following question:

Was the alternative cause for the previous occurrence of PHL criteria being met found to be the disease under study (eg, chronic or progressing malignant disease, severe infection or liver disease), or did the subject meet PHL criteria prior to starting study treatment and at first on-study treatment visit, as described in Appendix A6A 6

If **No**: Follow the process described in Appendix A4.1.

If **Yes**: Determine if there has been a significant[#] change in the patient’s condition compared with when PHL criteria were previously met.

If there is no significant change, no action is required.

If there is a significant change, follow the process described in Appendix A4A 4.

A ‘significant’ change in the patient’s condition refers to a clinically relevant change in any of the individual liver biochemistry parameters (ALT, AST or total bilirubin) in isolation or in combination, or a clinically relevant change in associated symptoms. The determination of whether there has been a significant change will be at the discretion of the Investigator; this may be in consultation with the AstraZeneca Physician if there is any uncertainty.

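### Appendix III A7 sends some repeat potential Hy's Law cases to A4.1, the process for patients who do not meet the criteria; the reference should be to A4.2

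*Combined protocol and SAP*

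**What the plan says.** Appendix III sets out what sites do when liver tests rise. PHL means AST or ALT at or above 3 × ULN together with total bilirubin at or above 2 × ULN (A2).

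A7 deals with repeat episodes. It is "applicable when a patient meets PHL criteria on study treatment, and has already met PHL criteria" at a previous on-treatment visit. It asks one question about the earlier episode: was it attributed to the disease under study, or is this the A6 situation (PHL already met before treatment and at the first on-treatment visit)?

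- If the answer is No: "Follow the process described in Appendix A4.1".
- If the answer is Yes: no action without a significant change; with one, the text points to A4 as a whole.

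A4 has two subsections.

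- A4.1 opens "If the patient does not meet PHL criteria the Investigator will" and lists two actions: "Inform the AstraZeneca representative that the patient has not met PHL criteria" and "Perform follow-up on subsequent laboratory results according to the guidance provided in the Clinical Study Protocol".
- A4.2 opens "If the patient does meet PHL criteria the Investigator will". Its steps include "Monitor the patient until liver biochemistry parameters and appropriate clinical symptoms and signs return to normal or baseline levels" (or for as long as is medically indicated), "Investigate the aetiology of the event and perform diagnostic investigations as discussed with the Study Physician", and completion of three liver case report form modules.

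**The concern.** The No branch names the wrong half of A4. A patient reaches it only by meeting PHL criteria, and it leads to the instructions for patients who do not.

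The branch also matters clinically. It holds the repeat episodes whose predecessor was not put down to the disease under study. That includes earlier episodes for which no alternative cause was found, where drug-induced liver injury is the open question, as well as those blamed on another drug. If the reference is followed as written, these patients get a lighter process than patients on the Yes branch with a significant change, whose earlier episode was disease-related or fell under A6. At stake are the completeness of the work-up and the documentation of a possible liver-safety signal.

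**Working it through.** There is no figure to reproduce. The check compares each section's entry condition with where A7 sends the patient.

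1. **Who is in A7.** PHL met now, on treatment, and PHL met at an earlier on-treatment visit. Every A7 patient therefore meets PHL criteria at the time of decision.

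2. **Who fits A4.1 and A4.2.**

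| Section | Entry condition | Can an A7 patient satisfy it? |
|---|---|---|
| A4.1 | PHL not met | Never |
| A4.2 | PHL met | Always |

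The overlap between A7 and A4.1 is empty. A4.2 is the only A4 subsection that fits.

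3. **What A4.1 would have the site do.** Its first action is a statement to the company representative that contradicts the finding that brought the patient to A7. Its second is follow-up of later laboratory results under the general protocol guidance.

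4. **The two branches compared.**

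| Answer in A7 | Earlier episode | Sent to | Result for a patient who meets PHL |
|---|---|---|---|
| Yes, significant change | Disease under study, or A6 situation | A4 as a whole | A4.2 |
| Yes, no significant change | As above | No action | None |
| No | Anything else, including no alternative cause found | A4.1 | A process whose condition is not met |

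5. **What a literal reading puts at risk.** Three A4.2 steps are expressly prescribed only there: monitoring to normal or baseline, diagnostic investigation agreed with the Study Physician, and the liver form modules. The first overlaps partly with A4.1's laboratory follow-up, with the liver tests that Section 4.0 schedules on Day 1 of each cycle and at end of treatment, and with A3's repeat blood draw for qualifying local results. The second overlaps partly with A5's search for an alternative explanation.

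6. **Could this be a reading error from the PDF?** Two neighbouring references in A7 are garbled (A6A 6 and A4A 4). The reference to A4.1 is clean and names a subsection that exists, so nothing on the page suggests an artefact.

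7. **How many patients.** Maximum accrual is 30 + 6 = 36 (Section 16.22). Exposure needs three things in one patient: a first on-treatment PHL episode, a second one, and a first episode that leads to No. The expected number is 36 × P(first episode) × P(second, given first) × P(No, given both). The documents give none of these probabilities. The only firm range is 0 to 36, but a product of three conditional events makes the low end by far the more plausible.

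**The case against.** The strongest reply is that the mistake corrects itself. A4.2 is triggered by its own opening condition, it is the next subsection after A4.1, and an investigator who has just established PHL is unlikely to report the opposite. A careful site may well end up in A4.2. This stands as a reason to doubt the harm. It does not make the reference right, and a safety procedure should not rely on sites noticing that its instruction cannot apply.

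The second reply is that other text limits the damage, and this largely stands. Section 4.0 footnote 5 sends results meeting both thresholds to this appendix. A3 requires the company representative to be told when the identification criteria are met. A5 says that it applies to every PHL case, and it requires Study Physician review within three weeks and the decision on SAE reporting. Section 10.4 requires SAE reporting independently. None of these corrects the reference.

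Three firmer inferences are tempting, and the documents do not support them.

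- A reader might infer that the branch leaves A5 fully intact because A5 claims all PHL cases. That is contestable: A7 makes the need for follow-up, review and assessment of a repeat depend on its own question. Equally, if A5 is protected by its own wording, so is A4.2.
- A reader might count which A4.2 steps are covered elsewhere and treat the count as exact. The sections do not match closely enough. For example, A4.2 asks about PHL at any visit before treatment, whereas A7's question also requires PHL at the first on-treatment visit and refers to A6, which is limited to patients with liver metastases.
- A reader might blame this reference for the absence of the liver form modules from the Section 18.1 timetable. They are absent there for first episodes too, and correcting A7 would not add them.

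**Conclusion.** The reference is wrong as written. A7 admits only patients who meet PHL criteria, its No branch leads to a process conditional on not meeting them, and no other text corrects this. That conclusion rests on the wording of A4 and A7 alone.

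The consequence is possible but not shown. Faced with an instruction that cannot apply, a site might stop, move to A4.2, or follow A4.1's lighter process; the documents do not settle which. A reader might infer that suspected drug-induced liver injury would go unreviewed or unreported. The separate duties in A3, A5 and Section 10.4 do not support going that far.

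On the assumption that repeat, non-disease-related PHL is uncommon, few or no patients would be affected. The primary endpoint, sample size, error rates and decision rule are untouched. This is a low-severity correction to an operative safety instruction.

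**What to change.** In the No branch of Appendix III A7, replace the reference to A4.1 with a reference to A4.2 and A5. Naming A5 also removes doubt about whether the review and assessment step applies to repeat episodes. Make the change at the next amendment and reissue the appendix to sites.

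The cost is one cross-reference. It adds no patients, and no tests beyond those that A4.2 already requires for PHL cases.
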